After Part 1, patients will continue in open-label Part 2 to receive dasiglucagon for 21 days. Additional CHI treatments can be introduced during Part 2 if needed, if up-titration of dasiglucagon is not possible because of undesirable side effects or if the maximum dose level (70 µg/hr) has been reached. Gradual transfer from IV glucose to oral and gastric carbohydrates should be initiated in Part 2, enabling weaning of IV glucose and hospital discharge. Patients will continue to be hospitalized until IV GIR is weaned off; however, as soon as local site criteria for discharge are met, patients can be discharged to continue the treatment period at home. Planned visits can be converted to telephone visits if appropriate, at the investigator's discretion. On Day 25, the End of Treatment Visit will take place, and based on the investigator's confirmation of continued positive benefit-risk balance, patients will be offered the opportunity to participate in the long-term extension trial (Trial ZP4207-17106) to continue dasiglucagon treatment. Patients who do not enter the long-term extension trial will have a Follow-up Visit 28 days after their last dose of trial drug. [Figure 1](#) describes the study design.

No Interim Analysis is planned.

Figure 1

Abbreviations: Min = minimum

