3.4. Treatments Administered

During the part 1, cross-over period, patient will receive Dasiglucagon and Placebo. During Part 2, patients will receive only Dasiglucagon.

Part 1 dispensing unit configuration: 3 vials containing dasiglucagon, 4 mg/mL in a 3 mL vial containing 1 mL of drug product or placebo in a 3 mL vial containing 1 mL of drug product. Dasiglucagon and matching placebo will be provided in the form of solution for injection for subcutaneous administration through an infusion pump.

As long as the patient is receiving IV glucose, the PG will be measured and reviewed hourly using a hand-held PG meter. The IV GIR will be titrated to achieve glycemia of at least 70 mg/dL (3.9 mmol/L) (a minimum GIR will be established as the rate up-titrated after the patient drops at least once below 70 mg/dL [3.9 mmol/L]). When the patient is no longer on IV GIR, the PG will be checked according to local practice, but at least 3 times daily. The PG will be measured using the same trial-supplied hand-held PG meter during the entire trial.

Additionally, blinded CGM will be started 24 hours prior to randomization (using the Dexcom G4 system) and continued until the end of Part 2.

Dosing of dasiglucagon will approximate continuous infusion by delivering small doses at frequent intervals via the infusion pump. The adjustment of trial drug dosing is closely linked to the PG level achieved, which in turn will govern the IV GIR. In Part 1 the algorithm in Table 1 should be used.

The pump administers 0.000025 mL/dose ~ 0.1 µg/dose (4 mg/mL formulation):

- 10 µg/hr ~ 0.5 µg every 3 min
- 20 µg/hr ~ 1 µg every 3 min
- 30 µg/hr ~ 1.5 µg every 3 min
- 40 µg/hr ~ 2µg every 3 min
- 50 µg/hr ~ 2.5µg every 3 min
- 60 µg/hr ~ 3µg every 3 min
- 70 µg/hr ~ 3.5µg every 3 min

Table 1 Algorithm to maintain plasma glucose

Plasma Glucose (mg/dL)	Plasma Glucose (mmol/L)	Action
<50	<2.8	Give 200 mg/kg of dextrose as a bolus and increase IV GIR by 2 mg/kg/min
50-59	2.8-3.3	Increase IV GIR by 2 mg/kg/min
60-69	3.3-3.9	Increase IV GIR by 1 mg/kg/min
70-80	3.9-4.4	No change
81-90	4.4-5.0	Reduce IV GIR by 0.5 mg/kg/min
91-100	5.0-5.5	Reduce IV GIR by 1 mg/kg/min
101-120	5.5-6.7	Reduce IV GIR by 1.5 mg/kg/min
>120	>6.7	Reduce IV GIR by 2 mg/kg/min

Abbreviations: GIR = glucose infusion rate; IV = intravenous

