The IV GIR will be reviewed, evaluated, and adjusted (if indicated) every hour according to the above PG-driven algorithm to maintain a PG of >70 mg/dL (>3.9 mmol/L). Rechecks of PG are allowed.

Part 1 (Crossover, double-blind, randomized, placebo-controlled)

The starting dose of trial drug is 10 μ g/hr at $t=0$. Every 2 hours ($t=2, 4, 6$, etc.), the dose will be increased by an additional 10 μ g/hr until either:

- The patient is totally weaned off IV glucose, or
- Plasma glucose during the last 2 hours was constantly above 120 mg/dL (6.7 mmol/L), or
- IV GIR has not decreased despite 2 sequential dose increments of trial drug (in this situation, the dose of trial drug should be maintained until the IV GIR can be further decreased or until crossover or the end of Part 1),
- The maximum dose of 70 μ g/hr is reached, AEs emerge that are considered to be related to dasiglucagon (e.g., nausea/change in feeding pattern or increased vomiting) that are limiting further dose escalation

The 2-hour dose-adjustment interval will allow drug plasma levels to approach steady-state before the dose is further increased. The cumulative dose will not exceed 1.26 mg over the first 24 hours and 1.68 mg for each of the subsequent 24-hour periods.

At the time of crossover from the first 48-hour period to the second 48-hour period, the trial drug will again be titrated from the starting dose of 10 μ g/hr, and IV GIR will be set to the rate obtained at the end of the run-in period which corresponds to the last value obtained before randomization and titrated accordingly.

Part 2 (Open label)

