After Part 1, patients will continue in open-label Part 2 to receive dasiglucagon for a further 21 days. Since treatment allocation during Part 1 remains blinded, all patients are required to initiate dasiglucagon dosing at 10 μ g/hr in Part 2, while IV GIR should be started at the rate obtained at the end of the run-in period which corresponds to the last value obtained before randomization. During Part 2, the dasiglucagon dose, the amount and route of administration of carbohydrates (IV GIR, parenteral nutrition, gastric carbohydrate infusions, and carbohydrates from oral feeds) can be adjusted at the discretion of the investigator. The PG should be monitored at least hourly to adjust the IV GIR as appropriate and to avoid hypoglycemia. Additional concomitant medications, including somatostatin analogs and/or sirolimus/mTOR inhibitors, may be introduced at the investigator's discretion if the maximum dose level of dasiglucagon (70 μ g/hr) has been reached or if further up-titration is not possible due to undesirable side effects.

Adjustment of total carbohydrate administered (IV glucose, parenteral nutrition, carbohydrate infusions, and carbohydrates from oral feeds) should continue throughout this period according to local practice to maintain PG levels in the range of 70 mg/dL to 120 mg/dL (3.9 - 6.7 mmol/L). The aim will be to obtain stable glucose levels with minimum rescue/hypoglycemia-preventative carbohydrates administered by invasive routes, and to encourage/optimize oral feeds, and achieve weaning off IV glucose. Regardless of their discharge status, all patients will be offered the opportunity to participate in the long-term safety extension trial (ZP4207-17106), providing the investigator attests to the positive benefit-risk balance of continued dasiglucagon treatment.

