6.1.7. Derived Variables

- **Day 1** = First day of Treatment (Placebo or Dasiglucagon) during Part 1. Study day will be calculated with respect to Day 1.
- **Treatment period**

As primary and secondary endpoint assessments are not performed at planned visits but continuously during the study, we have to define treatment periods. Those will then be used to assign a treatment period to an evaluation.

Treatment periods created will be:

- Part 1 – Treatment period 1: First 48-hours treatment period
- Part 1 – Treatment period 2: Second 48-hours treatment period
- Part 1 – Last 12 hours per treatment period
- Part 2

[Table 4](#) describes the derivation for each of those treatment periods.

Table 4: Derivation of Treatment Periods

Part	Time Point	Treatment Period (TP)	Start date	End date
Part 1		TP1	Day 1	Last exposure treatment period 1
		TP2	First exposure treatment period 2	Last exposure treatment period 2
Part 1	Last 12-hour/24-hour per TP	TP1	End date minus 12 hours/24 hours	Last exposure treatment period 1
		TP2	End date minus 12 hours/24 hours	Last exposure treatment period 2
Part 2			Day 5 first exposure	End of study exposure

Abbreviations: TP1 = treatment Part 1, TP2 = treatment Part 2

- **Study Week:** to be defined for Part 2 only
 - A 7-day period derived for displays of events related to CGM and/or SMPG results, gastric carbohydrate administrations, health care outcomes, and other assessments that may occur between clinic visits where a defined study week is needed.

The study weeks will be derived as follows:

Table 5: Study weeks

Study Week	Start	End
Week 1	Day 5 first exposure	Start + 167 hours 59 minutes
Week 2	End date week 1 + 1 minute	Start + 167 hours 59 minutes
Week 3	End date week 2 + 1 minute	Start + 167 hours 59 minutes

- **Change from baseline** = value at current time point – value at baseline.
- **TEAE** = an AE with an onset at the time of or following the start of treatment with the trial drug (dasiglucagon or placebo) through the Follow-up visit or Early Termination visit, whichever occurs first.
- **Weighted Mean IV GIR:** AUC will be calculated using linear trapezoidal method and divided by the length of the time period in minutes. The weighted mean IV GIR endpoint is expressed as glucose in mg/kg/min. This will be calculated over last 12 hours of each treatment period and over last 48 hours of each treatment period during Part 1.

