- **Weighted Mean IV GIR threshold:** This variable will be assigned “Yes” when the Weighted Mean IV GIR calculated over 12 hours period is not missing and < 10mg/kg/min and will be assigned “No” when value calculated will be $\geq 10\text{mg/kg/min}$.
- **Z-scores:** For subjects who are less than 2 years of age, WHO growth charts will be used to calculate Z-scores, as described here: 'www.cdc.gov/nccdphp/dnpao/growthcharts/resources/sas-who.htm'. For subjects who are greater than or equal to 2 years of age, Z-scores will be derived based on the SAS program in link 'www.cdc.gov/nccdphp/dnpao/growthcharts/resources/sas.htm' by using SEXN, Age in months ((VSDAT-ADSL.BRTHDT)/30.4375) and corresponding weight/height at baseline measurements.

- **PK Clearance:**

$$CL/f \text{ (L/h)} = R_0/C_{ss}$$

where R_0 = infusion rate (pmol/h) and C_{ss} = concentration at steady state (pmol/L), weight
($1\mu\text{g}/\text{kg}/\text{hr} = 295.7 \text{ nmol}/\text{kg}/\text{h}$)

- **Primary endpoint IV GIR:** Values from SDTM.EX where EXTRT="IV GLUCOSE INFUSION", not including the "IV GLUCOSE BOLUS".
- **Total amount of carbohydrates received:**

Calculated as the sum of carbohydrates received via IV glucose infusion or bolus, as part of total parenteral nutrition, via oral route and via NG tube or gastrostomy. This average daily value will be used in analysis calculated as the sum of carbohydrates received divided by number of days in corresponding period. As IV glucose infusion is recorded in mg/kg/min, for each analysis period, the total amount received will be calculated as:

$$\text{IV glucose infusion (mg)} = \text{Infusion rate recorded in CRF} \times \text{WGT} \times \text{TIME}$$

with WGT = weight at beginning of the analysis period, TIME = duration of analysis period in minutes

IV glucose infusion or bolus are reported in SDTM.EX with EXTRT in "IV GLUCOSE INFUSION" or "IV GLUCOSE BOLUS".

Carbohydrates received via oral route, via NG tube or gastrostomy are reported under Carbohydrates administration eCRF.

Total parenteral nutrition is reported under Carbohydrates administration eCRF selecting observations specified as part of TPN.

- **Nightly gastric carbohydrates to treat hypoglycemia** = amount of gastric carbohydrates (g) given between midnight and 6 am inclusive to treat hypoglycemia.

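### SAP 6.1.7 multiplies one unspecified recorded infusion rate by the length of the whole analysis period, which does not give the IV glucose infused when the rate is titrated or weaned

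*SAP*

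**What the plan says.** SAP 6.1.7 defines total carbohydrates as the sum of IV glucose (infusion and bolus), parenteral nutrition, oral intake and NG tube or gastrostomy intake, expressed per day. Infusions are recorded in mg/kg/min, so the section converts them to an amount. For each analysis period the amount in mg is the product of three terms: "Infusion rate recorded in CRF", WGT and TIME, "with WGT = weight at beginning of the analysis period, TIME = duration of analysis period in minutes".

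The analysis periods are long. SAP 8.2.1 uses 48 hours per treatment period for H12. SAP 8.3.1 reports the Part 2 amounts by week and over three weeks.

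The rate is not constant over such periods:
- In Part 1, SAP 3.4 has the IV GIR "reviewed, evaluated, and adjusted (if indicated) every hour". The changes in its Table 1 run from "Reduce IV GIR by 0.5 mg/kg/min" up to 2 mg/kg/min, in either direction.
- At crossover, "IV GIR will be set to the rate obtained at the end of the run-in period", and it is titrated from there.
- In Part 2, "IV GIR should be started at the rate obtained at the end of the run-in period". SAP section 3 then says: "Gradual transfer from IV glucose to oral and gastric carbohydrates should be initiated in Part 2, enabling weaning of IV glucose".

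SAP 6.1.7 also defines a weighted mean IV GIR (area under the curve divided by the length of the period): "This will be calculated over last 12 hours of each treatment period and over last 48 hours of each treatment period during Part 1". The carbohydrate formula does not refer to it.

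**The concern.** The units work: mg/kg/min x kg x min = mg. The difficulty is that TIME is fixed as the length of the whole window, while the rate is an unindexed CRF entry. A 48-hour window with hourly review can hold many recorded rates, and the SAP does not say which one enters. Multiplying any single one by the whole window gives the amount infused only if that rate happens to equal the time average. In Part 2 the window also includes time after the infusion has stopped. The definition of time to weaning in SAP 6.1.7 accepts that some infants may later need IV glucose again.

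What is at stake is the infusion component of H12, which is the only test after the primary in the fixed sequence (SAP 6.1.3), and the same component of the Part 2 carbohydrate summaries. A confirmatory endpoint should have one derivation that two programmers would reproduce.

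**Working it through.** **The plan's own figures.** The SAP gives no worked value for this formula, so there is none to reproduce. The nearest design figure is the 89% power in SAP 3.2 (n = 12, difference 7.5, SD of differences 7.36, one-sample t-test). At two-sided 0.05 it reproduces as 89.4%. It concerns the primary endpoint and does not use the carbohydrate formula.

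**When the formula is right.** Let rate_i apply for minutes m_i, with the m_i adding up to TIME and rate_i = 0 while off infusion.

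- Amount infused (mg) = WGT x sum(rate_i x m_i).
- SAP formula (mg) = rate x WGT x TIME.
- The two agree exactly when rate = sum(rate_i x m_i) / TIME, the time-weighted mean.

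**Inputs for one illustration**

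- From the documents: start 18.5 and plateau 11 mg/kg/min (the cited study's medians, SAP 3.2); a reduction of 0.5 mg/kg/min, the smallest change in Table 1; hourly review; a 48-hour window.
- Assumed: 4 kg; a reduction at every hourly review, the first at 1 h, until 11 is reached; then constant to 48 h. The two medians describe a group of infants in the 24 hours before and after IV glucagon was started. Using them as one infant's starting rate and plateau is also an assumption.

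**Time-resolved amount**

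- Number of reductions: (18.5 - 11) / 0.5 = 15.
- Excess over 11 in the first 15 hours: 7.5 + 7.0 + ... + 0.5 = 0.5 x (15 x 16 / 2) = 60 (mg/kg/min x h).
- Mean GIR over 48 h: 11 + 60/48 = 12.25 mg/kg/min.
- Amount per day: 12.25 x 4 x 1440 / 1000 = 70.56 g/day.

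**The SAP formula with a single rate**

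| Rate used | mg/kg/min | g/day (rate x 4 x 1.44) | Against 70.56 |
|---|---|---|---|
| First in window | 18.5 | 106.56 | +51.0% |
| Last in window | 11 | 63.36 | -10.2% |
| Time-weighted mean | 12.25 | 70.56 | 0 |

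The percentages do not depend on weight; the grams are proportional to it.

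**Part 2.** The weighted mean is defined only for windows in the Part 1 periods, so for a Part 2 week or the three-week window the SAP offers no mean to substitute. TIME is not limited to minutes on infusion either.

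**The case against.** The strongest reply is that this is incomplete wording and not a wrong rule. The same entry defines the endpoint as a sum of carbohydrates received, and the formula can be seen as a unit conversion that any programmer would apply record by record. Alternatively, the rate can be read as the 48-hour weighted mean defined in the same section. In the example, that mean, taken by linear trapezoid on hourly records, gives 70.11 g/day against 70.56, a difference of 0.45 g/day or 0.6%.

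Neither reading is in the text. The first contradicts it: TIME is expressly the analysis-period duration, and weight is likewise taken once, at the start of the period. The second adds something unstated and has no counterpart in Part 2. Where the authors want a time-resolved calculation they write one, as for the weighted mean GIR and the extent of hypoglycemia.

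Parts of the reply do stand. The size shown depends on an assumed GIR course and on two choices of rate that no section proposes. Nothing shows that the analysis program follows the formula literally.

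A reader might also infer that the infusion part of the H12 contrast is zero by design, because both crossover periods are planned to start at the run-in rate. That would need the first rate to be the one used, which the SAP does not say. SAP 8.1.1 also records that some infants did not start both periods at the same rate, and boluses, parenteral nutrition and feeds enter the total as well.

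**Conclusion.** The formula is wrong as written and should be corrected. It gives the amount infused only when the rate is the window's time-weighted mean, which SAP 6.1.7 does not state for this endpoint and does not define for Part 2.

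The defect is confined to the IV infusion component. It reaches H12 and the Part 2 carbohydrate summaries, for which SAP 8.3 plans no inference. The primary endpoint is derived separately, so neither it nor its power is affected.

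The illustrated errors of +51% and -10% show that the choice of rate matters. They rest on the assumed course and are not estimates of bias in this trial. The documents do not support a conclusion that the H12 result is biased in a particular direction, or that the programmed derivation is wrong; the actual effect on H12 is unknown.

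**What to change.** Replace the formula in SAP 6.1.7 by:

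IV glucose infusion (g) = sum over infusion records i of (rate_i x weight x minutes of record i inside the analysis window) / 1000, with zero while off infusion.

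Boluses are added separately, as already planned. Use this one rule for both Part 1 periods, each Part 2 week and the three-week window.

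State also whether the site 101 between-part GIR values (SAP 8.1 and section 10) are excluded from this total. SAP 8.1 removes them from analyses based on IV GIR, but the H12 text in SAP 8.2.1 is silent. If they are excluded, either carry the last valid rate forward or take those minutes out of both numerator and denominator. Deleting the records alone would count about 15 minutes as zero glucose, up to 15/2880 = 0.5% of a 48-hour window.

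The cost is a few lines of SAP text and a check of the matching program. No new data are needed: Protocol 11.2.3.2 already requires all IV GIR details, including boluses, to be recorded in the eCRF.

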11.2.1.2. Continuous Glucose Monitoring

Dexcom CGMs, configured and labeled for use in the trial, will be provided. In Germany, only the Dexcom G6 CGM will be used. Enrollment in Germany will start only after Dexcom G6 CGM is available.

For other countries: the Dexcom G4 may be used until all required approvals for use of the Dexcom G6 are obtained, but no later than to the end of 2020, when the Dexcom G4 will be taken off the market by the supplier. Patients enrolled thereafter will all be using the Dexcom G6 CGM. Patients who started in the trial using the Dexcom G4 CGM should continue using this device throughout the trial and should not switch to the Dexcom G6 device.

The CGM will be started at least 24 hours prior to randomization and will be used during Parts 1 and 2 in a blinded mode to evaluate efficacy in terms of hypoglycemic episodes. Short pauses of 1 to 3 days due to skin irritation or discomfort are allowed during Part 2 of the trial after consultation with the investigator.

The CGM device should be calibrated and used according to the manufacturer's instructions.

At each visit, the investigator will ensure that CGM data are downloaded from the patient's device. The procedure for download of CGM data will be described in the pharmacy manual/TMM.

The contract research organization (CRO) or delegate will handle the device sourcing, configuration for use in this trial, procedures for blinded data extraction, device service, and handling of potential returns.

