- **Event rate** = average of the weekly number (sum) of events/episodes, based on the number of weeks in the relevant period. Events include hypoglycemia, clinically significant hypoglycemia, gastric carbohydrate administrations, and SMPG readings.
- **Percent time (CGM)** = (number of minutes where PG at a pre-defined level / total number of minutes patient is wearing CGM) * 100%. For this calculation, one assessment of CGM will be considered having a 5-minute duration. The possible levels are:
 - **In range:** PG between 70-180 mg/dL (3.9-10.0 mmol/L), inclusive
 - **Hypoglycemia:** PG <70 mg/dL (3.09 mmol/L)
 - **Clinically significant hypoglycemia:** PG <54 mg/dL (3.0 mmol/L)
 - **Hyperglycemia:** PG >180 mg/dL (10.0 mmol/L)
- **Time to complete weaning off IV GIR:** Time from first exposure during Part 2 to stop of Glucose infusion. Complete weaning off IV GIR is defined as the first point in time when the patient has been off IV GIR for 12 hours. This definition is based on clinical considerations that 12 hours off IV GIR is considered a reasonable indication that patients can manage without IV GIR, even though some of them may need re-initiation of IV glucose at later point. In case of study withdrawal before having the event, patient will be censored at time of study withdrawal.
- **Time to actual hospital discharge:** Time from first exposure during Part 2 to discharge of hospital. In case of study withdrawal before having the event, patient will be censored at time of study withdrawal.

- **Time to pancreatic surgery** = Time from first exposure during Part 2 to pancreatic surgery. Pancreatic surgery event will be retrieved from Adverse Event or Medical History Form. Pancreatic surgery is defined as sub-total or total pancreatectomy with a cutoff of 95% or more. In case of study withdrawal before having the event, patient will be censored at time of study withdrawal.
- **Extent of hypoglycemia (AO_C_{glucose})** =

$$\sum_{k=0}^{X-1} \frac{(UL - PG_k) + (UL - PG_{k+1})}{2} \times (t_{k+1} - t_k)$$

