where UL is the upper limit for the hypoglycemia definition (70 mg/dL or 54 mg/dL); k is the k^{th} time point that glucose is measured using CGM; PG_k is the PG value in mg/dL on the k^{th} time point; and X is the end time point of the 3-week treatment period (Weeks 2-4). When $k = 0$, t_k is set to 0 and PG_k is the PG value corresponding to the start of the 3-week treatment period. Only PG values less than UL will be included in the calculation. If $PG \geq UL$ at the k^{th} time point and $PG < UL$ at the $k^{\text{th}}+1$ time point, then the extent of hypoglycemia for that interval will be determined as follows:

1. Estimate time point on x-axis where $PG = UL - 0.01$, as if a straight line were drawn between time points by using the following formula:

$$\hat{k} = \frac{(UL - 0.01) - b}{m}$$

Where b = y-intercept of line created by the coordinates (k^{th} time point, PG_k) and ($k^{\text{th}}+1$ time point, PG_{k+1}) and m = slope of that line.

2. Substituting PG_k with UL and t_k with $t_{\hat{k}}$, the formula for the estimated interval below UL is as follows:

$$\frac{(UL - UL) + (UL - PG_{k+1})}{2} \times (t_{k+1} - t_{\hat{k}})$$

Similar methodology would be utilized if $PG < UL$ at the k^{th} time point and $PG \geq UL$ at the $k^{\text{th}}+1$ time point, with the estimate of the time point where PG crosses the UL threshhold being estimated for $t_{\hat{k}+1}$.

If the time period between two timepoints is greater than 1 hour then no interpolation will be performed and no area will be calculated over this timeperiod.

If PG results from the k^{th} time point are missing, then $k-1$ scores will be used and the weight will be $t_{k+1}-t_{k-1}$.

The extent of hypoglycemia calculated as above will then be divided by the total duration of CGM assessments calculating as summing all $t_{k+1}-t_k$ duration used in previous formulae. Time points for which $PG>UL$ will be included in the total duration. This variable will then be used the endpoint evaluation.

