8.3.1. Primary Analyses for Secondary Endpoints

Part 1 (Day 1 to 4, for each 48-hour treatment period)

- Weighted Mean IV GIR for each 48-hour treatment period during Part 1 (dasiglucagon or placebo administration). This endpoint will be analyzed using the same mixed-model regression approach as the one used for primary endpoint and removing IV GIR data that are not valid for site 101. No sensitivity analysis on this endpoint.

- Weighted Mean IV GIR below 10 mg/kg/min in the last 12 hours of each treatment period during Part 1 (yes/no) (dasiglucagon or placebo administration). For this analysis a generalized estimating equation (GEE) method with logit link function will be used using below program and removing IV GIR data that are not valid for site 101.

```
PROC GENMOD;  
  CLASS PATIENT PERIOD TRT;  
  MODEL OUTCOME= PERIOD TRT / LINK=LOGIT DIST=BINOMIAL ;  
  REPEATED SUBJECT=PATIENT/ WITHIN=PERIOD TYPE=CS;  
  LSMEANS TRT / ILINK CL EXP DIFF;  
  ESTIMATE "DASIGLUCAGON versus PLACEBO" TRT 1 -1 ;  
RUN;
```

Part 2 (Day 5 to 25, assessed from the start of treatment in part 2)

If patient needs a pancreatectomy, this will occur only during the Part 2 of the study. If pancreatectomy was done before randomization, it will not be taken into account. Only patients with pancreatectomy during the study will have censored values.

The evaluation of the Part 2 endpoints will then be impacted by pancreatectomy. To be able to assess only treatment effect as primary analysis the following rules will be applied:

- SMPG-detected episode, Carbohydrates administrated, CGM-detected episode, CGM percent time endpoint and extent of hypoglycemia will be set to missing after pancreatectomy (whatever percentage of pancreatectomy).
- Time to complete weaning off IV GIR and time to actual hospital discharge will be censored at time of pancreatectomy (whatever percentage of pancreatectomy).

Following endpoints will be described by week and over the three weeks period.

- Time to complete weaning off IV GIR. Only patient without complete weaning off IV GIR at start of Part 2 will be included in this analysis. Kaplan-Meier estimates will be given for each of the three weeks treatment period.
- Rate of SMPG-detected hypoglycemia episode, defined as number of hypoglycemic events (PG <70 mg/dL or 3.9 mmol/L).
- Rate SMPG-detected Clinically significant hypoglycemia episode, defined as number of events <54 mg/dL (3.0 mmol/L).

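### Part 2 CGM hypoglycaemia episode rates are averaged over fixed study weeks rather than CGM wear time, so a permitted sensor pause counts as time without episodes

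*SAP*

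**What the plan says.** SAP 6.1.7 (Derived Variables) has a single definition of event rate: the "average of the weekly number (sum) of events/episodes, based on the number of weeks in the relevant period". It covers hypoglycaemia and clinically significant hypoglycaemia, with no separate rule for episodes detected by CGM. Table 5 in the same section starts Week 1 at first Part 2 exposure and ends each week at "Start + 167 hours 59 minutes", that is, 168 hours by the clock. The text above that table says these weeks serve CGM-related as well as SMPG-related events.

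The other CGM endpoints in SAP 6.1.7 use a different denominator:

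- Percent time is divided by the "total number of minutes patient is wearing CGM", each reading counting as 5 minutes.
- Extent of hypoglycaemia "will then be divided by the total duration of CGM assessments". On gaps: "If the time period between two timepoints is greater than 1 hour then no interpolation will be performed", and no area is taken over them.

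On reporting, SAP 8.3.1 states: "Following endpoints will be described by week and over the three weeks period". Table 4 closes Part 2 at "End of study exposure".

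Both protocol versions (11.2.1.2) foresee gaps: "Short pauses of 1 to 3 days due to skin irritation or discomfort are allowed during Part 2 of the trial". They set no limit on the number of pauses.

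**The concern.** The same sensor gap is handled in two ways. It leaves the denominator of percent time and extent, but stays in the denominator of the episode rate as though the infant had been watched and had no episodes. For any infant who has episodes, this pushes the rate down.

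The results are shown week by week, so the timing of a pause matters. A pause in week 1 looks like a later rise, and a pause in week 3 looks like a fall on treatment. Percent time and extent for the same infant would show neither if the true rate is constant. A reader comparing the CGM endpoints could then see a disagreement that has nothing to do with hypoglycaemia. With 12 infants, individual and weekly values will be read closely.

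No planned analysis would reveal it. SAP 8.3 allows no imputation for these endpoints. SAP 8.3.2 only lifts the pancreatectomy rule and adds a paracetamol exclusion for percent time below 70 mg/dL.

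**Working it through.** **Plan's own figure.** The documents give no expected CGM episode rate, pause frequency or wear time, so there is nothing to reproduce. The 89% power statement concerns the primary endpoint and is not used here.

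**Inputs.** Study week of 7 days (SAP Table 5); Part 2 of 21 days, or three weeks; pause of 1 to 3 days (Protocol 11.2.1.2); 12 infants (SAP 3.2). Assumptions not in the documents: a constant true rate *r* per week, pauses unrelated to hypoglycaemia, and each pause within one study week. The 7 episodes per week and 30-minute episodes below are illustrative.

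**One infant.** With *p* days paused, the sensor detects *r*(7 - *p*)/7 episodes in that week and *r*(21 - *p*)/7 over three weeks.

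- SAP rate, affected week: *r*(7 - *p*)/7, relative error -*p*/7
- SAP rate, three weeks: *r*(21 - *p*)/21, relative error -*p*/21
- Wear-time rate: episodes / days worn x 7 = *r*, whatever *p* is

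| Pause | Affected week | Three weeks |
|---|---|---|
| 1 day | -1/7 = -14.3% | -1/21 = -4.8% |
| 2 days | -2/7 = -28.6% | -2/21 = -9.5% |
| 3 days | -3/7 = -42.9% | -3/21 = -14.3% |

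The relative error does not depend on *r*, except that an infant with no episodes has no error.

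**Example.** True rate 7 per week, 3-day pause in week 1. The SAP rule gives 4, 7, 7 and (4 + 7 + 7)/3 = 6.0. Per wear time it is 7, 7, 7 and 18 episodes / 18 days x 7 = 7.0. Had the same pause fallen in week 3, the SAP rule would give 7, 7, 4.

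**Percent time in the same infant.** With 30-minute episodes, a full week gives 7 x 30/(7 x 1440) = 2.08% and the paused week 4 x 30/(4 x 1440) = 2.08%.

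**Group of 12 with equal rates.**

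| Who pauses | Mean for that week | Three-week mean |
|---|---|---|
| 1 infant, 1 day | (1/7)/12 = 1.2% lower | (1/21)/12 = 0.4% lower |
| 1 infant, 3 days | (3/7)/12 = 3.6% lower | (3/21)/12 = 1.2% lower |
| 3 infants, 3 days, same week | 3 x (3/7)/12 = 10.7% lower | 3 x (3/21)/12 = 3.6% lower |

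**Alternative reading.** Suppose the SAP means weeks with any CGM data. One 3-day pause leaves 4 days of data in a 7-day week, so that week still counts in full and the error is unchanged.

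**The case against.** The strongest reply is about size. These are single-arm, descriptive secondary endpoints. At 7 episodes per week and Poisson counts, the relative standard error of a 12-infant mean is 1/sqrt(84) = 10.9% for one week and 1/sqrt(252) = 6.3% over three, before any between-infant variation. One infant's pause lies well inside that, and three infants pausing 3 days in the same week only reach about one standard error for the week. This stands: a misleading trend is realistic mainly for individual infants. But the error is systematic in direction and avoidable.

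Second, the SAP does not say whether a partly observed week counts as a fraction. That is fair for a truncated week: because Part 2 closes at the end of exposure, the three-week rate can be read as exposure time. It does not reach a sensor pause during exposure, since nothing in the definition refers to wear.

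Third, percent time and extent are themselves undisturbed only if pauses are unrelated to hypoglycaemia. For extent, SAP 6.1.7 also has a rule that uses the preceding value with a longer weight when a result is missing, and does not say how it ranks against the 1-hour rule. Both remarks are correct. The 1-hour rule is the natural one for a gap of days, and the mismatch in denominators remains either way.

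Fourth, a minimum wear time for the episode rate alone would create a new difference from percent time and extent. This is a reasonable caution and is dealt with in the fix.

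**Conclusion.** The concern holds. Followed as written, the SAP counts unobserved sensor time as free of episodes in both CGM-detected episode rates, but not in the other CGM endpoints. One permitted pause understates an infant's rate by 14-43% in the affected week and 5-14% over three weeks. The effect on a group mean is small for one pausing infant (at most 3.6% for a week and 1.2% over three weeks) and larger if several pause together.

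These figures rest on a constant rate and non-informative pauses, and the group figures also on equal rates. How often infants pause is not given, so the overall effect cannot be stated. Other CGM data loss acts in the same way. The primary and key secondary analyses, alpha and power are untouched. The definition should be changed because the affected endpoints are named measures of hypoglycaemia and the direction favours the drug.

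**What to change.** In SAP 6.1.7, give the CGM-detected episodes (<70 and <54 mg/dL) their own rate: number of episodes divided by CGM wear time, scaled to 7 days, using the wear minutes already derived for percent time.

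Also state:

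- **Truncated weeks.** Observed time is the denominator: wear time for CGM, observed days for SMPG. This covers early end of exposure and the week of a pancreatectomy, after which SAP 8.3.1 sets CGM-detected episodes to missing.
- **Minimum wear for a weekly rate to be shown**, for example 72 hours. A week with one permitted 3-day pause keeps 4 x 24 = 96 hours and is retained. Let all episodes and all wear enter the three-week rate, and print wear time beside the weekly CGM endpoints so that a suppressed rate can be understood next to percent time and extent.
- **SMPG.** Keep the weekly rate and show the weekly number of readings beside it, which SAP 6.1.7 already lists under event rate. Add a footnote that checks can fall from hourly on IV glucose to as few as 3 per day after weaning (Protocol 10.2), so a falling SMPG count may partly reflect fewer checks. A time denominator would not correct that.

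The cost is SAP wording and one changed denominator in the program; no new data are needed. The downside is less stable weekly rates at short wear. At 7 episodes per week (one per day, Poisson) the relative standard error for one infant is 1/sqrt(days worn): 38% at 7 days, 50% at 4, 58% at 3 and 100% at 1. That is the reason for a minimum, and weeks below it would not be shown.
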